## 12.5 Automatic Measurements Analysis (Part 2)

### 12.5.1 Statistical Methods Values and Characteristics

**Two-way ANOVA** – test used to detect any overall differences between related means.

ANOVA characteristics

UAB Ligence	Clinical Investigation Report	2021-04-09
		Rev: 1.0

Source of variation	Degrees of Freedom	Mean Square
Patient	n - 1	MSS
Cardiologist	t - 1	MSR
Error (Patient x Cardiologist)	(n - 1)(t - 1)	MSSR
Error (Cardiologist)	nt(m - 1)	MSE

ANOVA variance components

Estimates of Variance Components
$\hat{\sigma}_S^2 = \frac{MSS - MSE}{mt}$
$\hat{\sigma}_R^2 = \frac{MSR - MSSR}{mn}$
$\hat{\sigma}_{SR}^2 = \frac{MSSR - MSE}{m}$
$\hat{\sigma}_e^2 = MSE$

**Standard Error of Measurement** – a measure of how much same measurements made by different physicians are spread around a “true” score. SEM in Two-way repeated measures ANOVA includes both the variability among raters’ measurements and within raters’ measurements.

$$SEM = \sqrt{\frac{MSR + (n - 1)MSSR + n(m - 1)MSE}{mn}}$$

**Minimal Detectable Change** – minimal amount of change that is required to distinguish a true change from a change due to variability of measurement or random error. MDC is derived from SEM and calculated as confidence interval. In this analysis 95% confidence interval will be used.

$$MDC_{95} = 1.96 * \sqrt{2}SEM$$

## 12.5.2 Data analysis

Two-way ANOVA will be employed in this analysis to prepare for further investigation. Inter-rater reliability and SEM will be calculated from the results of ANOVA. SEM will be used to get minimal detectable change. Absolute difference between the automated system measurement and mean of the raters’ measurements will be compared with MDC as the primary endpoint of the analysis to check if there is a significant difference between physicians and automated system. The same difference will be compared with SEM as the secondary endpoint. Same analysis will be conducted with measurements of the 4th rater. Results will allow to compare the accuracy of automated systems measurements and physicians’ measurements.

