## 12 Statistical Methods

### 12.1 Statistical Hypotheses

UAB Ligence	Clinical Investigation Report	2021-04-09
		Rev: 1.0

The following hypotheses will be tested with the statistical methods:

1. The manual functionalities of Ligence Heart provide equally accurate tools for echocardiography evaluation compared to other state of the art CE marked medical software.
2. Automatic functionalities of Ligence Heart software perform echocardiography image analysis with non-inferior accuracy compared to a cardiologist.
3. Automatic functionalities of Ligence Heart software perform echocardiography image analysis with lower intra-rater variability compared to a cardiologist.
4. Automatic functionalities produce measurement values faster than a cardiologist.

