## 12.3 Statistical Analysis

Data analysis will be carried out with Python  $\geq 3.6$  with statistical package pingouin  $\geq 0.3.10$ . Pingouin will be used to calculate ANOVA results (calculations provided in <https://pingouin-stats.org/generated/pingouin.anova.html#pingouin.anova>). All other calculations will be done according to formulas provided in this section.

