LVESV4A	100.0 ± 0.0	100.0 ± 0.0		56	2	Yes
LVEDV2A	96.3 ± 5.03	100.0 ± 0.0	0.16	54	4	Yes

UAB Ligence	Clinical Investigation Report	2021-04-09
		Rev: 1.0

[figure not shown]
LVESV2A	96.3 ± 5.03	100.0 ± 0.0	0.16	54	4	Yes
RAA	94.44 ± 6.11	98.15 ± 3.59	0.31	54	4	Yes
RVB	98.18 ± 3.53	98.18 ± 3.53	1	55	3	Yes
RVM	100.0 ± 0.0	94.55 ± 6.0	0.08	55	3	Yes
RVOTPD	100.0 ± 0.0	100.0 ± 0.0		58	0	Yes
RVEDA	98.18 ± 3.53	100.0 ± 0.0	0.32	55	3	Yes
RVESA	98.18 ± 3.53	100.0 ± 0.0	0.32	55	3	Yes

*ORG - original rater group consisting of three board certified cardiologists; FC – fourth board certified cardiologist. \*P values for measurements that fall 100% in agreement in both groups are undefined. The “Pass” column specifies whether measurement accuracy is considered to be non-inferior. In order for the automated measurements to pass, a P value of > 0.05 or undefined is required which means that there is no significant difference in variation between Ligence Heart and FC measurements.*

UAB Ligence	Clinical Investigation Report	2021-04-09
		Rev: 1.0

[figure not shown]
Figure 1. Comparison of LigenceHeart and cardiologist measurements in agreement with the original rater group

**Figure 1.** The X axis represents the number of studies that were measured in agreement with ORG by Ligence Heart or FC. Each Y axis position represents a different measurement. 95% CIs are shown for Ligence Heart only. Ligence Heart 95% CI lower bound is at or above FC performance. ORG - original rater group. FC - fourth cardiologist.

[figure not shown]
UAB Ligence	Technical file	2021-04-09
		Rev: 1.0

Supplementary figure 1. Correlation of measurements between all raters

Electronic version of the document is valid, printed version of the document is not controlled. The document is stored at: Ligence Cloud storage unit. Internal company document.

UAB Ligence	Clinical Investigation Report	2021-04-09
		Rev: 1.0

[figure not shown]

**Supplementary figure 1.** Pearson correlation coefficients between all raters is shown. A value of -1 is assigned whenever the correlation is not calculated, either because it would be a duplicate or because it would compare measurements with the same rater and run. OR - original rater, R1 and R2 - run 1 and run 2, FC - fourth cardiologist, LH - Ligence Heart. Run 1 and run 2 refers to different repeats of the study by the same rater.

[figure not shown]

UAB Ligence	Clinical Investigation Report	2021-04-09
		Rev: 1.0

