### 16.2 Automatic functionalities (Part 2)

Due to the fact that echocardiography is prone to considerable inter- and intra-observer variability, it was important to perform comparison of the automatic measurements using data from multiple board certified cardiologists. The first three cardiologists established the acceptable intra- and inter-observer variation ranges while the fourth cardiologist and Ligence Heart were used as independent raters with accuracy calculated as the number of times measurements fell within acceptable variation range in the selected studies. Non-inferiority of automatic measurements accuracy to a cardiologist was established by conducting the t-test and assuring p-values are  $> 0.05$  which proves that any differences are non-significant. All of the measurements passed the required performance threshold, and for 7 out of 21 automatic measurements, both Ligence Heart and FC had full agreement with the ORG.

Conversely, Ligence Heart automatic functionalities did not return a value for at least one study in 11 measurements, however, there was a sufficient number of studies for all measurements where automatic analysis value was returned to ensure statistical power. The reason for no value being returned in a particular study has to do with the automatic predictions not passing quality thresholds which are employed in each step of the automatic functionalities (classification, cardiac phase or cycle detection and measurement prediction confidence). This ensures that a lower number of false values is provided to the user of the medical device and serves as a safety mechanism by reducing the number of potential false positive findings.

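### Part 2 non-inferiority is declared by a t-test and a p > 0.05 pass rule that section 12 does not contain, in place of the named MDC primary, and non-significance does not show non-inferiority

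*Protocol*

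**What the plan says.** The Protocol is a combined document: sections 5 to 12 hold the plan, and sections 15 and 16 hold the results.

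**Plan.** Hypothesis 2 (12.1) is that the automatic functions "perform echocardiography image analysis with non-inferior accuracy compared to a cardiologist"; no margin is given. Section 12.5.1 defines SEM and MDC95 = 1.96 × √2 × SEM. Section 12.5.2 takes the absolute difference between the automated value and the raters' mean: "measurements will be compared with MDC as the primary endpoint of the analysis to check if there is a significant difference between physicians" and the automated system. It adds "The same difference will be compared with SEM as the secondary endpoint" and "Same analysis will be conducted with measurements of the 4th rater", and says that the results will permit a comparison of accuracy. It states no test, margin or pass rule between device and fourth rater. Section 12.3 assigns the ANOVA to a software package and continues: "All other calculations will be done according to formulas provided in this section". No t-test appears in section 12.

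**Results.** Section 15.2 counts, for device and FC, the studies lying within the limits of variation of the original three raters, with FC as benchmark. The Table 3 footnote sets the rule: "In order for the automated measurements to pass, a P value of > 0.05 or undefined is required". Section 16.2 concludes: "Non-inferiority of automatic measurements accuracy to a cardiologist was established by conducting the t-test and assuring p-values are" above 0.05. The Figure 1 caption states another criterion, that the lower bound of the device's 95% CI is at or above FC's result. Section 16.3 then treats the expected performance as proven.

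**The concern.** The step that turns agreement counts into a verdict on hypothesis 2 is not in the plan. It first appears next to the data that it judges.

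The rule also runs in the wrong direction. A difference test with p > 0.05 says only that the data could not separate the two readers, and the less information there is, the easier that becomes. Rows where both readers agree in every study have no p-value at all and are passed by default. The readers also measured the same studies, so a paired comparison is called for.

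At stake is the main pre-market claim for the automatic functions. The question is whether the reported results support a statement that they are non-inferior to a cardiologist.

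**Working it through.** **Inputs.** Table 3: percentage in agreement and its half-width for device and FC, p-value and number of studies, for 21 measurements. Percentages × n were rounded to counts (LAD: 55/58 and 58/58; RAA: 51/54 and 53/54).

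**1. Reproduce the printed p-values.** Unpaired t-test on the 0/1 agreement indicator, with a and b studies in agreement out of n:

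- SSE = a(n − a)/n + b(n − b)/n
- s² = SSE/(2n − 2)
- t = [(a − b)/n] / √(2s²/n), with 2n − 2 degrees of freedom

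LAD: SSE = 55 × 3/58 + 0 = 2.845; s² = 2.845/114 = 0.02496; SE = √(2 × 0.02496/58) = 0.02933; |t| = 0.05172/0.02933 = 1.76; p = 0.081 (printed 0.08). All 14 printed p-values are reproduced to two decimals. The other 7 rows (AoS, STJ, IVSd, LVEDD, LVESD, LVESV4A, RVOTPD) have zero variance and no p-value. The test used was therefore unpaired.

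**2. What LAD's pass allows.** Difference = −3/58 = −5.17 points. Wald SE = √(0.9483 × 0.0517/58) = 2.91 points. Lower 95% limit = −5.17 − 1.96 × 2.91 = −10.9 points. Because FC agreed in all 58 studies, the paired Wald interval is the same. One more miss (54/58) gives p = 0.042 and a fail.

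**3. How the rule behaves.** With FC at 100%, three misses pass and four fail at every sample size tried:

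| n | device agreement with 3 misses | p, 3 misses | p, 4 misses |
|---|---|---|---|
| 20 | 85.0% | 0.075 | 0.036 |
| 54 | 94.4% | 0.080 | 0.042 |
| 58 | 94.8% | 0.081 | 0.042 |

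A smaller study would thus pass a worse device. As an illustration with assumed true rates (device 90%, reader 98%, n = 58, independent readings), summing the binomial probabilities of all outcomes that pass gives a pass for that measurement in about 55% of studies.

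**4. Apply the Figure 1 caption to Table 3.** Lower bound = device percentage − half-width, compared with FC. LAD: 94.83 − 5.70 = 89.13 < 100, not met. LAV4A: 98.21 − 3.47 = 94.74 ≥ 94.64, met. Over all rows it is met by 9 of 21 (AoS, STJ, LAV4A, IVSd, LVEDD, LVESD, LVESV4A, RVM, RVOTPD). The caption is therefore untrue for 12 rows.

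**5. Internal figure.** The 15.2 text gives the device's lowest agreement as 93.1%, for RAA; Table 3 gives 94.44% (51/54). The former equals 54/58, so the two cannot share a numerator and denominator.

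**The case against.** **The fourth rater was planned.** This stands. Sections 7.2 and 12.5.2 give the fourth rater the same MDC analysis, and the agreement counts plausibly build on it. A reader might infer that the whole comparison with FC was invented afterwards, but the documents do not support that. Only the between-reader test and its pass rule are new.

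**Section 12.3 is not a strict list.** This partly stands. Section 12.4.2 plans a Pearson correlation whose formula is not printed either, so the absence of a t-test formula is weak evidence alone. The point rests on 12.5.2, which names a different primary and no between-reader test.

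**Detail may sit in an unseen SAP.** A required share of studies might. That does not cover a document that names one primary and then declares success on a different rule.

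**The caption may be a slip.** If upper bound was meant, all 21 rows comply, but that is again a check for no detected difference. As written it contradicts Table 3.

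**Stronger readings that fail.**

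- MDC95 might seem to require 95% of studies inside the limit, so that LAD and RAA fail. No such share is stated. MDC95 is built for the difference of two single readings. Against a mean of six readings the variance lies between SEM² × (1 + 1/6) and SEM² × (1 + 1/3) for exchangeable normal readers, so expected coverage is about 98.4% to 99.0%.
- Twenty-one tests at 0.05 might seem to inflate the error rate. Passing here means non-significance, so multiplicity adds false failures. The danger is false acceptance.

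**Conclusion.** The concern holds in this form: hypothesis 2 was accepted on an unpaired t-test with a p > 0.05-or-undefined rule that is absent from section 12 and cannot show non-inferiority, while the named MDC primary is not reported as such. By that rule 21 of 21 rows pass, 7 of them without a p-value; by the document's own Figure 1 criterion 9 of 21 do. LAD is compatible with a deficit of up to about 10.9 points.

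The row counts and p-values need only Table 3 and rounding to whole studies. The 55% figure rests on assumed rates and independence. Whether the limits of variation are the MDC is not stated, so no verdict on the MDC primary itself can be drawn. Nor do the data show that the device is inferior: in LAV4A and RVM it agreed more often than FC. What is missing is support for the positive claim.

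**What to change.** Leave 12.5.2 unchanged as the record of the plan; rewriting it now would set a rule with the results in view. In sections 15.2, 16.2 and 16.3:

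1. Report the named primary, the MDC comparison, for device and fourth rater, and say whether the limits of variation are the MDC.
2. Disclose the t-test and its pass rule as not pre-specified.
3. Replace the p > 0.05 rule with the paired within-study difference in agreement (device minus FC) and its 95% CI for each of the 21 measurements, labelled post hoc. Any margin must be declared and justified as post hoc. Choose an interval method that remains informative when both readers are at 100%, where the Wald width is zero.
4. Correct the Figure 1 caption and reconcile the two RAA figures.
5. Replace the statements that non-inferiority was established, shown or proven with: no significant difference was detected; non-inferiority was not formally tested.

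The cost is a re-analysis of existing data, which needs the study-level agreement records because Table 3 alone does not give the pairing for every row, and a less favourable conclusion.

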### 15.3 Intra-rater variability and time comparison

Comparing measurements for each ORG member between different runs resulted in median R of 0.85 (IQR 0.73 - 0.88), 0.81 (IQR 0.73 - 0.87) and 0.78 (IQR 0.66 - 0.84) for original raters 1, 2 and 3, respectively. Due to Ligence Heart automatic measurements being determined by the input, Ligence Heart had no variation in measurements between different runs and had R of 1.0 for all measurements (Table 4), resulting in significantly lower intra-rater variability ( $p < 0.05$ ).

ORG members on average took  $12:58 \pm 3:18$  minutes to analyze the same measurements in 58 TTE studies while Ligence Heart was significantly faster, taking on average  $2:59 \pm 1:02$  minutes to analyze the same studies ( $p < 0.05$ ).

**Table 4.** Comparison of correlation coefficients between different runs in original rater group and Ligence Heart.

Label	OR1 Run 1 vs Run 2	OR2 Run 1 vs Run 2	OR3 Run 1 vs Run 2	Ligence Heart Run 1 vs Run 2
RAMAD	0.86	0.86	0.82	1
AoA	0.57	0.73	0.65	1

UAB Ligence	Clinical Investigation Report	2021-04-09
		Rev: 1.0

AoS	0.86	0.83	0.83	1
STJ	0.51	0.77	0.59	1
AAo	0.73	0.46	0.72	1
LAD	0.83	0.83	0.8	1
LAV4A	0.85	0.92	0.84	1
IVSd	0.88	0.62	0.42	1
LVPWd	0.66	0.35	0.41	1
LVEDD	0.92	0.86	0.89	1
LVESD	0.83	0.88	0.78	1
LVEDV4A	0.88	0.81	0.84	1
LVESV4A	0.93	0.91	0.88	1
LVEDV2A	0.93	0.87	0.87	1
LVESV2A	0.96	0.92	0.88	1
RAA	0.9	0.89	0.88	1
RVB	0.75	0.74	0.78	1
RVM	0.73	0.75	0.71	1
RVOTPD	0.88	0.77	0.77	1
RVEDA	0.75	0.68	0.66	1
RVESA	0.7	0.68	0.61	1

*Pearson correlation coefficients between different runs for the same rater are shown. Since Ligence Heart performs all measurements automatically and the output is completely determined by input, it has a correlation coefficient of 1 for all measurements. Run 1 and run 2 refers to different repeats of the study by the same rater. OR1 – original rater one; OR2 – original rater two; OR3 – original rater three.*

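### The Part 2 agreement limit suits a difference of two single readings but is applied to one reading against a mean of six, and it widens with rater noise, so agreement says little for about five of the 21 measurements

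*Protocol*

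**What the plan says.** Section 12.5.1 defines a standard error of measurement that "includes both the variability among" raters and the variability within them. It then sets "MDC_{95} = 1.96 * \sqrt{2}SEM", describes this as the "minimal amount of change that is required to distinguish a true change from a change due to variability of measurement or random error", and adds that "MDC is derived from SEM and calculated as confidence interval", at the 95% level.

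Section 12.5.2 names what is held against that limit: "Absolute difference between the automated system measurement and mean of the raters"' measurements, which "will be compared with MDC as the primary endpoint of the analysis". It continues: "The same difference will be compared with SEM as the secondary endpoint". The fourth rater's measurements get the same analysis.

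Section 7.2 assigns three physicians to the modelling and the fourth to validation, each reading every study twice. Section 15.2 confirms six reference values per measurement per study in 58 studies. A measurement passes if the p-value against the fourth cardiologist exceeds 0.05 or is undefined. Table 4 (Section 15.3) gives same-rater repeatability: "Pearson correlation coefficients between different runs for the same rater are shown".

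**The concern.** There are two separate problems.

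First, the factor √2 is right when both sides of a difference carry the full error of one reading. Here one side is an average of six readings and carries much less error, so the limit is wider than its 95% label implies.

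Second, the limit is built only from the cardiologists' own disagreement, and no clinical cap is stated. The noisier a measurement is in human hands, the easier it is to agree with. For the noisiest ones the limit may span most of the spread between patients, and then an output carrying no patient information would also agree.

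This matters because the comparison is the declared primary endpoint of Part 2 and the basis of the accuracy conclusion in Sections 15.2 and 16.2.

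**Working it through.** **Inputs.** SEM and MDC formulas: Section 12.5.1. Three raters, two runs, 58 studies: Sections 7.2 and 15.2. Run-to-run R: Table 4. Agreement rates and pass rule: Table 3.

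**1. What SEM is.** Putting the expected mean squares into the printed SEM formula gives SEM² = σR² + σSR² + σe², the variance of one reading by a random rater around the true value. The multiplier 1.96 × √2 = 2.772 is therefore the 95% limit for two single readings.

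**2. Limit for the comparison actually made.** For one reading against the mean of 3 raters × 2 runs:

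Var = SEM² + (σR² + σSR²)/3 + σe²/6 = (1 + g) SEM², with g between 1/6 (all error within rater) and 1/3 (none within rater).

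| g | matching 95% limit | 2.772 ÷ that limit | inside 2.772 SEM | inside, with bias of 1 SEM |
|---|---|---|---|---|
| 1/6 | 1.96√1.167 = 2.12 SEM | 1.31 | 99.0% | 94.9% |
| 1/3 | 1.96√1.333 = 2.26 SEM | 1.22 | 98.4% | 93.7% |

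At 1 SEM, the planned secondary limit, an exchangeable reader falls inside in 61% to 65% of studies and a reader biased by 1 SEM in 46% to 47%. The contrast is about 15 to 18 points there, against 4 to 5 points at the MDC.

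**3. Estimated variance components.** The table treats the components as known, but σR² rests on three raters. Simulating the planned ANOVA (58 studies, 3 raters, 2 runs) with an exchangeable new reader, the MDC covers about 97% to 98% when σR² is 30% to 50% of SEM². The matching limit of step 2 then covers about 92% to 94%. With small σR² both behave as tabulated.

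**4. Constant output.** Suppose the device returned the population mean for every patient. With inter-rater reliability ρ and total variance scaled to 1, SEM² = 1 − ρ, and the difference from the raters' mean has variance ρ + (1 − ρ)g. So

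agreement = 2Φ(2.772√(1 − ρ) / √(ρ + (1 − ρ)g)) − 1.

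Part 2 inter-rater reliability is not reported. The mean Table 4 R is used as a proxy, roughly an upper bound, since differences between raters lower reliability and would raise the constant's agreement. For LVPWd, R = (0.66 + 0.35 + 0.41)/3 = 0.473:

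- g = 1/6: 2.012/0.749 = 2.69, giving 99.3%.
- g = 1/3: 2.012/0.805 = 2.50, giving 98.7%.

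| Measurement | mean R | constant agrees | device, Table 3 |
|---|---|---|---|
| LVPWd | 0.47 | 98.7–99.3% | 96.55% |
| STJ | 0.62 | 95.1–96.0% | 100% |
| AAo | 0.64 | 94.5–95.5% | 98.28% |
| IVSd | 0.64 | 94.4–95.3% | 100% |
| AoA | 0.65 | 93.9–94.9% | 98.28% |
| RVOTPD | 0.81 | 80.8–81.7% | 100% |
| LVEDD | 0.89 | 66.0–66.5% | 100% |

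If LVPWd reliability were as high as its best single rater (0.66), the constant would still agree in 93.4% to 94.4%. With the step 2 limit in place of the MDC, it would still agree in about 96% for LVPWd, so changing the multiplier does not remove this problem.

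**5. Link to the pass rule.** The LVPWd row reproduces: 56/58 = 96.55 ± 4.70, and a paired t-test against 58/58 gives p = 0.159 (printed 0.16). Against 58/58, 55/58 passes (p = 0.083) and 54/58 fails (p = 0.045). In a simulation with rater-specific noise from Table 4, a constant reaches at least 55/58 with probability about 0.999 for LVPWd, 0.90 for IVSd, 0.85 for AAo and 0.84 for STJ. The fourth cardiologist scored 100% on all four.

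**The case against.** The strongest reply is that nothing in the protocol requires 95% agreement. The fourth cardiologist is judged by the same limit, and passing depends on the comparison between the two. That stands: the wide limit loosens both readers alike. A reader might infer that the device met a 95% target only because the limit was generous, but no such target is stated. What remains is that a loose limit pushes both towards 100% and leaves little room to tell them apart.

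A reader might also infer that Table 3 as a whole shows the width of the limit and nothing about the device. The documents do not support that. By the same calculation a constant would agree in about 81% for RVOTPD and 66% for LVEDD, while the device is reported at 100% for both. Nor is the device shown to behave like a constant: Section 15.2 gives a median device–cardiologist correlation of 0.74 (IQR 0.59–0.83) and plots individual readings. Correlation is not the pass rule and does not show bias, but it is evidence against that reading. Section 16.2 itself singles out LVPWd as the most variable measurement.

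Two cautions also stand. Table 4 is same-rater correlation, so it does not directly show how well cardiologists agree with one another. Section 15.2 does not define the variation limits behind Table 3; taking them as the MDC of Section 12.5.2 is an inference.

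**Conclusion.** The point holds in two bounded parts.

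- **Multiplier.** With known variance components the planned limit is about 22% to 31% too wide for the comparison made, and holds about 98% to 99% of an exchangeable cardiologist's readings (about 97% to 98% if σR² is 30% to 50% of SEM²). The consequence is weaker discrimination between device and cardiologist.
- **Noise scaling.** The agreement rate is uninformative for roughly five measurements: LVPWd clearly, and STJ, AAo, IVSd and AoA on the proxy used. This does not extend to all 21. The boundary is gradual: RVESA, at mean R 0.66, gives 93% to 94%.

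Assumptions: normal errors; the automated value treated as one reading; the constant placed at the population mean; mean Table 4 R standing in for Part 2 inter-rater reliability; Table 3 limits equal to the MDC. Over a wider range of reliability, a constant would agree in 99.7–99.9% at 0.35, 98.4–99.0% at 0.5, 95.9–96.8% at 0.6, 91–92% at 0.7 and about 82% at 0.8.

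**What to change.** All steps use existing readings.

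1. In Sections 12.5.1 and 12.5.2 use 1.96 × √(SEM² + (σR² + σSR²)/3 + σe²/6), with components from the planned ANOVA. State that it can undercover (about 92% to 94% in the simulation) when σR² is large, because it rests on three raters. Otherwise keep the MDC but stop describing it as a 95% limit for this comparison.
2. Since step 1 leaves the noise scaling in place, add a paired continuous comparison for each measurement: |device − mean of the three raters| minus |fourth cardiologist − mean of the three raters|, with a 95% confidence interval. Give mean bias and limits of agreement for both. Label these post hoc where results already exist.
3. Report the planned secondary comparison with SEM, which Section 15.2 does not show.
4. Limit the accuracy conclusion for LVPWd, STJ, AAo, IVSd and AoA accordingly, and state which limit Table 3 used.

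The cost is analysis and rewriting. Reported agreement will look less favourable, and the added analyses carry the weight of post hoc work only.
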